**Eligibility criteria include the following:**

- Age 6 to less than 18 years at the enrollment visit
- Physician diagnosis of asthma, and
- History of an asthma exacerbation in the previous 12 months, defined as either:
  - Treatment with systemic corticosteroids,\* or
  - Increase in rescue medication use (i.e., abuterol or inhaled corticosteroid) for 24 hours or more, or
  - One or more missed school days due to asthma symptoms, or
  - An unscheduled visit for asthma at either a physician's office, urgent care, hospital emergency room, or
  - Hospitalization for asthma.

*\*In the event of a recent exacerbation treated with systemic corticosteroids or requiring hospitalization, the first study visit will be postponed until two weeks after the last dose of systemic corticosteroids (i.e., prednisone or prednisolone).*

These criteria should ensure a study population with sufficient disease burden, since several prior studies in children have identified these risk factors as significant predictors of poor asthma control and poor future outcomes. Indeed, several prior studies in children have identified a recent exacerbation as the strongest risk factor for subsequent exacerbations regardless of disease severity or use of controller medications. In the third iteration of the NHLBI Severe Asthma Research Program (**SARP**, [name] co-investigator), exacerbations occurred in 39.7% of enrolled children by one year (unpublished data), similar to reports in other cohorts. In SARP, an exacerbation in the previous year was also associated with an 8.94-fold increase in the odds of future exacerbation by one year (95% CI: 4.37, 18.69). Poor asthma symptom control at baseline was similarly associated with increased odds of future exacerbation (OR 2.65, 95% CI: 1.44, 4.82), but there was no additive effect with prior exacerbation. Therefore, we have elected to enroll participants irrespective of asthma symptom control. This will not only facilitate enrollment of participants, but will also promote symptom heterogeneity (which is essential for symptom clustering) and the likelihood of biomarker detection (since inflammation will also be heterogeneous).

**Exclusion criteria for Option 1, a single study visit with telephone/email and electronic medical record follow-up for up to 48 weeks, include:**

- Pregnancy,
- Current smoking,
- Congenital disorders or deformities of the chest wall, lungs or airways,

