## J. Outcome measures

Asthma exacerbations are an outcome of interest for all participants.

For participants enrolled in the 48-week cohort study, the primary outcome is corticosteroid treatment responsiveness, assessed 14 days after systemic triamcinolone administration (at visit 2). Responsiveness will be determined from the mean difference in the Asthma Control Questionnaire (**ACQ**) score between visit 1 (baseline) and visit 2 (14 days), with a reduction of 0.5 considered a minimally important difference.

The secondary outcome for participants enrolled in the 48-week cohort study is quality of life, assessed by the PROMIS Pediatric Asthma Impact Scale (**PAIS**) at visits 3, 4 and 5. As with all PROMIS measures, the PAIS is scored on the T-score metric, with higher scores reflecting more of the concept being measured. On the T-score metric, 50 is the mean of the reference population and 10 is the standard deviation; thus scores of 40 and 60 are one standard deviation lower and higher than the mean of the reference population, respectively.

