## L. Procedural details

**Asthma control evaluation.** Asthma control and associated respiratory symptoms will also be assessed with the Asthma Control Questionnaire (**ACQ**) and the Asthma Control Test (**ACT**). The ACQ can be completed by children down to 6 years with strong measurement properties when administered by a trained interviewer. The ACQ is sensitive to short-term changes in asthma control and has well-documented reliability and cross-sectional and longitudinal validity in diverse asthma populations across a wide range of severities. This 7-item questionnaire includes questions related to daytime and nocturnal symptoms, short-acting bronchodilator use, and lung function during the clinic visit on that day. A higher score indicates poorer asthma control. The ACT can be completed directly by children 12 years and older; children 6-11 years will complete the Childhood ACT (**C-ACT**). Both tools have been extensively validated and have excellent measurement properties. For both tests, individual items about respiratory symptoms (5 and 7 in total for ACT and C-ACT, respectively) are summed; scores of 19 or less reflect uncontrolled asthma.

**PROMIS symptom questionnaires.** Symptoms will be assessed with validated PROMIS measures for children. PROMIS measures will be completed directly by children age 8-21 years, with caregiver assistance for children 6-7 years. The following PROMIS short-form measures will be utilized:

- Pediatric Life Satisfaction (4a)
- Pediatric Meaning and Purpose (4a)
- Pediatric Physical Stress Experience (4a)
- Pediatric Physical Activity (4a)
- Pediatric Positive Affect (4a)
- Pediatric Psychological Stress Experiences (4a)
- Pediatric Family Relationships (4a)
- Pediatric Asthma Impact (8a)
- Pediatric Anger (5a)
- Pediatric Anxiety (8a)
- Pediatric Depressive Symptoms (8a)
- Pediatric Fatigue (10a)
- Pediatric Peer Relationships (8a)

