Because LTA is aimed at characterizing transition over time, it requires variability in all variables. Therefore, we will perform LTA with patient-reported symptoms (global, mental, social and physical health categories) and measures of asthma disease activity (ACQ, ACT, lung function, exhaled nitric oxide, blood eosinophils) measured at baseline and visits 3, 4 and 5 (**see Appendix 1**). Age, sex, race, ethnicity, socioeconomic status, medications, exposures and allergic sensitization measured at the baseline visit will be considered stable and treated as covariates in the LTA model. All participants will be included in the analysis since missing data for the variables are handled in the procedure, with data assumed to be missing completely at random. The test of the null hypothesis that data are missing completely at random (Missing Completely At Random test in the SAS LTA procedure) will be evaluated; if non-significant, missingness does not affect the interpretation of the results. The number of classes will be statistically determined using the Bayesian information criterion (**BIC**) and class prevalence if BICs are of a similar magnitude, to avoid a solution leading to low prevalent groups (<5%). To assess the stability of the group structure, goodness of fit of the “constrained” LTA model in which identical item-response probabilities across time are estimated (i.e., the same cluster structure is forced into multiple time points) will be compared with the “unconstrained” LTA model in which item response probabilities are estimated at each time point. To further address sex as a biological variable, models will also be fitted by sex, with statistical comparison of results observed in boys and girls. All analyses will be performed with SAS software version 9.4 (SAS Institute) using the PROC LTA procedure.

The primary outcome will be assessed after assignment of individuals to the latent classes that they had the highest probability of belonging to (based on the posterior probability provided by the model at baseline). A straightforward analysis of the primary outcome will follow and involves comparison of the proportion of children achieving a minimally importance difference in ACQ of at least 0.5 in each of the latent classes via a Chi-Square test.

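### Baseline ACQ helps form the symptom classes and is also the starting value of the ACQ responder outcome, so a class difference in the primary test need not be differential steroid response

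*Combined protocol and SAP*

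**What the plan says.** Section U (aims 1-3) builds the classes by latent transition analysis from patient-reported symptoms and "measures of asthma disease activity (ACQ, ACT, lung function, exhaled nitric oxide, blood eosinophils) measured at baseline and visits 3, 4 and 5". Section L lists 13 PROMIS short forms, one of them Pediatric Asthma Impact. It describes the ACQ this way: "This 7-item questionnaire includes questions related to daytime and nocturnal symptoms, short-acting bronchodilator use, and lung function during the clinic visit on that day". Each child is put in the most probable class, "based on the posterior probability provided by the model at baseline".

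Section J defines the primary outcome from the ACQ "score between visit 1 (baseline) and visit 2 (14 days), with a reduction of 0.5 considered a minimally important difference". Section U turns this into a responder proportion and says the analysis "involves comparison of the proportion of children achieving a minimally importance difference in ACQ of at least 0.5 in each of the latent classes", using a chi-square test. No baseline term is attached to that test. Neither covariate list in Section U (one for the class model, one following the secondary outcome) includes baseline ACQ.

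Entry sets no minimum ACQ: "we have elected to enroll participants irrespective of asthma symptom control". Aim 2 in Section B expects the class with the poorest symptoms to respond least.

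**The concern.** One measurement does two jobs. Visit 1 ACQ, with other asthma reports from the same visit, helps decide which class a child joins, and it is also the value from which the fall is counted. Two effects follow even when triamcinolone works equally well in every class.

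- Regression to the mean: visit-specific error that raises baseline ACQ makes a worse class more likely and also enlarges the expected fall.
- Floor: a child who starts below 0.5 cannot fall by 0.5 if the scale starts at 0, and such children will mostly sit in the best-symptom class.

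Both raise the apparent response of the worst-symptom class relative to the best, which is mostly opposite to Aim 2. At stake are two errors of reading: taking a class difference for differential steroid response when it is not, and missing a truly poorer response in the worst-symptom class.

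**Working it through.** **1. The plan's own figure.** Power = 1 - F(7.815; 3 df, noncentrality N x W²). With N=147 and W=0.275 the noncentrality is 147 x 0.0756 = 11.12 and power is 0.808, as in Table 3. All 45 cells reproduce (largest gap 0.0014), and 173 x 0.85 = 147. The table is right as arithmetic, but it presumes that equal response gives equal responder proportions.

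**2. Regression to the mean.** Let the observed baseline be x, the mean m, the reliability r and the equal true fall 0.3. Without a floor, the expected observed fall is 0.3 + (1 - r)(x - m). With SD 1.0 (assumed) and r = 0.70, a child one SD above the mean is expected to fall 0.3 + 0.30 = 0.60, and one SD below 0.3 - 0.30 = 0.00. With r = 0.85 the values are 0.45 and 0.15.

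**3. Floor.** The share starting below 0.5 is Φ((0.5 - m)/1.0): about 1%, 7%, 16% and 31% at m = 3.0, 2.0, 1.5 and 1.0.

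**4. Simulation of the plan.** The documents give no ACQ mean, SD, reliability or expected fall, so all are assumed: SD 1.0, reliability 0.70 and 0.85, equal true fall 0.3, scores clipped to 0-6. A four-class latent transition model was fitted over baseline and visits 3-5, with 13 or 4 PROMIS indicators, modal baseline class and N=147. Further assumptions: PROMIS factor correlated 0.4 with severity; ACT and Asthma Impact correlated 0.7 with same-visit ACQ, and lung function 0.3; median splits; no covariates. There were 200 trials per scenario (Monte Carlo error up to 3.5 points). This approximates PROC LTA and is not a run of it. Rejection rates at a nominal 5%:

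| Mean ACQ | Planned test | Planned classes, only children with ACQ of at least 0.5 |
|---|---|---|
| 3.0 | 12-26% | 11-26% |
| 2.0 | 19-31% | 9-18% |
| 1.5 | 33-49% | 8-11% |
| 1.0 | 69-82% | 4-7% |

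At mean 3.0 the floor is negligible, so that row shows double use alone. At mean 1.0 the floor dominates. Restricting children without changing the classes does not remove double use.

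**5. Separating the mechanisms.** A simpler check fitted classes to the baseline visit only (N=147, SD 0.9, equal true fall 0.5, 300 trials). With no baseline error and no floor it rejected in 3%. Regression to the mean alone gave 14% (reliability 0.8) and 27% (0.7). The floor alone gave 70% at mean 1.2. Wherever error or floor was present, 86-100% of rejections had the worst-symptom class responding more.

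**6. Changing the class indicators** (model of step 4, all four means):

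- without ACQ and ACT: 7-27%
- also without Asthma Impact: 8-17%
- the latter, limited to ACQ of at least 0.5: 4-10%
- lung function dropped too: 4-13%, and 4-9% with the limit

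**7. Masking** (same model, reliability 0.8, means 1.0-2.0). The worst-symptom quarter truly falls 0.2 and the others 0.5. The worst class nevertheless shows a higher responder rate than the best in 49-90% of trials as planned. This drops to 30-62% without ACQ, ACT and Asthma Impact, and to 11-24% with the limit added.

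**The case against.** **The floor is not a statistical error.** If children starting below 0.5 cannot respond, responder proportions really do differ between classes, and rejecting equal proportions is correct. This stands: that part concerns interpretation. The regression part does not depend on it.

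**The largest rates need a low mean.** Section H expects many participants to have poor control, which argues against a mean near 1.0. This stands, and 69-82% should not be the headline.

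**The size is uncertain.** Several inputs were single assumed values, and the model leaves out the planned covariates and missing data from telephone visits. In the baseline-only check at mean 1.5 and reliability 0.8, rejection was 29% with zero true fall and 48-54% with a fall of 0.5. It was 98% with an equal 35% relative fall, where worse classes fall further in ACQ points. The direction is firm; the size is not.

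**Visits 3-5 dilute the link.** The simulation used all four visits and the link remained.

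**The bias opposes the hypothesis.** A reader might infer that the plan is tilted toward confirming Aim 2. The documents do not support that, since the artefact mostly runs the other way. The cost is a misleading opposite finding or a masked true one.

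**Option 2 numbers.** Only these children are dosed and attend visit 2, so fewer than 147 may be analysed. That is a separate matter and adds no weight here.

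**Conclusion.** The coupling is in the text and nothing in the plan corrects it. The primary chi-square can show a class difference when true response is equal, mostly in the direction opposite to Aim 2, and can hide a poorer response in the worst-symptom class. Under the stated assumptions at N=147, rejection is 12-26% from double use alone and 19-31% at mean ACQ 2.0. Higher rates at lower means come increasingly from the floor.

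A reader might infer that the test is invalid, or that its false-positive rate is about 80%. The documents support neither: they give no ACQ distribution, and the chi-square remains a correct test of equal observed proportions. What is not supported is reading its result, on its own, as differential steroid response. This should be fixed in the SAP; confidence in the size is moderate.

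**What to change.** Keep the Aim 1 classes and the planned chi-square. Pre-specify for Aim 2:

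1. The same chi-square with classes formed without ACQ, ACT and PROMIS Pediatric Asthma Impact, stating whether lung function, itself an ACQ item, stays in.
2. That comparison limited to baseline ACQ of at least 0.5, as a sensitivity analysis only. The limit keeps low-severity children with upward error: in baseline-only checks it moved the null contrast toward Aim 2 in about 62-70% of trials at means 1.0-1.5.
3. Responder rates by class and baseline ACQ band.

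If a worst-minus-best contrast is reported, give its estimate and 95% CI. Rank the classes on the 12 PROMIS measures other than Asthma Impact, after reverse-scoring the six that are favourable when high: Life Satisfaction, Meaning and Purpose, Physical Activity, Positive Affect, Family Relationships and Peer Relationships. Without reversal the average largely cancels.

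State that a planned-test difference will not be read as differential steroid response unless analysis (1) supports it by its own estimate and interval. Agreement in sign is too weak: in a baseline-only check, 40-72% of spurious opposite-direction results kept their sign in both supporting analyses. Even full agreement is supportive only, because there is no untreated control.

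Visit 2 ACQ regressed on class plus baseline ACQ is also supportive only, because it over-corrects. A logistic responder model with the same adjustment, keeping ACQ in the classes, rejected in 23-27% of baseline-only null trials at mean 1.5, about 99% of them toward Aim 2.

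Cost: SAP text and a second class model, no new data, and supporting classes that differ from those of Aim 1. Analysis (1) does not fully restore 5%. In (2), about 137 to 102 of 147 children remain at means 2.0 to 1.0 (147 x 0.933 and 147 x 0.691). Power at W=0.275 then falls from 0.81 to about 0.78-0.64. A class has fewer than 20 children in 1-10% of trials in (1) and 7-81% in (2), most often at mean 1.0.

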## **B. Study hypothesis/aims**

We propose a 48-week cohort study (N=173) to test the overarching hypothesis that symptom clusters and their associated inflammatory and metabolic pathways predict corticosteroid treatment responsiveness (primary objective outcome) and quality of life (patient-reported secondary outcome) in children 6 up to 21 years with exacerbation-prone asthma.

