### **Aim 1. Identify and phenotype symptom clusters and assess their temporal trajectories in children with exacerbation-prone asthma.**

Hypotheses: A cluster of children with the poorest physical, mental, and social health symptoms will be identified by latent class analysis; this cluster will have stable symptom presentations over time.

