### **Aim 2. Determine associations between symptom clusters and clinical outcomes in children with exacerbation-prone asthma.**

Hypotheses: Children with the poorest physical, mental, and social health symptoms will have the poorest corticosteroid treatment responsiveness and quality of life.

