## **T. Sample size**

The sample size is 173 participants age 6 up to 21 years, which accounts for a conservative attrition rate of 15% (final N=147). The following assumptions were used for sample size calculations:

- Identification of 4 symptom clusters resulting in 3 degrees of freedom,

- >80% desired power for a chi-square test of multiple proportions,
- Two-tailed significance level of 0.05 if the effect size (W) is small-to-medium by Cohen's convention and equivalent to W=0.275 (small effect: W=0.10, corresponding odds ratio=1.49; medium effect: W=0.30, corresponding odds ratio=3.45), and
- Sample size allocation ratio of 1-2 per cluster group and sample sizes of at least 20 per group.

The sample size calculations with the above parameters should achieve at least 80% power as shown in **Table 3**.

For the secondary outcome, The sample size of 173 children necessary for the primary outcome should achieve >85% power to detect a difference of 0.2 between group means (considered a small effect size  $d$ ) with standard deviation of 0.20. Power >80% is achieved if the mean difference between groups and associated standard deviation is slightly larger but still small (0.25-0.30). In our prior study of triamcinolone administration to children with asthma, mean ( $\pm$  standard deviation) quality of life scores (on a different instrument, the Asthma Quality of Life Questionnaire) were 6.17 ( $\pm$  0.75) and 5.07 ( $\pm$  0.99), respectively. If similar differences are noted between two symptom cluster groups, we should have >90% power for the primary outcome and >95% for the secondary outcome if the groups have at least 20 participants. With smaller group sizes of only 13 participants, power would be >81% and >89% for the primary and secondary outcomes, respectively.

Drop-out	df	Power if effect size is:				
		0.250	0.275	0.300	0.325	0.350
10% (N=156)	3	0.749	0.833	0.897	0.941	0.969
	4	0.703	0.795	0.867	0.920	0.956
	5	0.664	0.760	0.840	0.900	0.942
12.5% (N=151)	3	0.734	0.820	0.886	0.933	0.963
	4	0.687	0.780	0.855	0.911	0.949
	5	0.648	0.744	0.826	0.889	0.934
15% (N=147)	3	0.721	0.808	0.877	0.926	0.959
	4	0.674	0.767	0.844	0.903	0.943
	5	0.634	0.731	0.814	0.878	0.927

**Table 3.** Estimated power.

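### A significant omnibus chi-square does not by itself establish Aim 2's prediction that the poorest-symptom class responds worst; one prespecified comparison should be added.

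*Combined protocol and SAP*

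**What the plan says.** Three statements bear on this point, and they differ in how specific they are.

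- Section B, overarching hypothesis: "symptom clusters and their associated inflammatory and metabolic pathways predict corticosteroid treatment responsiveness". This has no direction. The title of Aim 2, which speaks only of associations, has none either.
- Section B, Aims 1 and 2: "A cluster of children with the poorest physical, mental, and social health symptoms will be identified by latent class analysis", and then "Children with the poorest physical, mental, and social health symptoms will have the poorest corticosteroid treatment responsiveness and quality of life". Together these pick out one class in advance and state a direction for it.
- Section U, plan for aims 1-3: each child is assigned to the most probable baseline class. The primary analysis then compares the "proportion of children achieving a minimally importance difference in ACQ of at least 0.5 in each of the latent classes via a Chi-Square test".

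Section T powers that test on the assumption "Identification of 4 symptom clusters resulting in 3 degrees of freedom". The actual number of classes is left to the data: "The number of classes will be statistically determined using the Bayesian information criterion", with class prevalence as a secondary criterion.

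Section U specifies no contrast between classes, no trend test, no post-hoc comparison for the primary outcome, and no rule for deciding which fitted class counts as poorest. Section T does quote power for a difference between two cluster groups, but Section U contains no test to match it.

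**The concern.** A chi-square test over four classes asks whether the responder proportions are all equal. Rejection says that they are not. It does not say which class differs or whether that class is higher or lower. Aim 2 says both.

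The reverse pattern is not far-fetched. Section U uses the ACQ score to form the classes, and the primary outcome is a fall of 0.5 in the same score. Children in the poorest class are likely to start with high ACQ scores and so have more room for such a fall. The primary p-value could then be significant because the poorest class responded better than the rest.

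The direction would have to be read from the observed proportions afterwards. There would be no interval for the comparison of interest and no prior rule for which class to look at. The classes are formed from many indicators (13 PROMIS measures in Section L, plus ACQ, ACT, lung function, exhaled nitric oxide and blood eosinophils), and one class need not be worst on all of them. Labelling the class after outcomes are known would leave the Aim 2 conclusion open to choice.

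**Working it through.** **Inputs from Section T.** 173 enrolled, 15% attrition, N=147 analysed; W=0.275; four classes, 3 df; alpha 0.05 ("Two-tailed significance level of 0.05 if the effect size (W) is small-to-medium by Cohen's convention"); class size ratio 1-2 with at least 20 per class. Responder rates by class are not given. Those below are assumptions, chosen so that W=0.275.

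**1. Reproduce the plan's figure.** Power = 1 − F(critical value; df, λ), where F is the noncentral chi-square distribution and λ = N·W² = 147 × 0.275² = 11.12.
- 3 df, critical value 7.815: power 0.808, as in Table 3. All 45 cells of Table 3 reproduce to within 0.0015.

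**2. What the test detects.** W² = Σ f_k(p_k − p̄)² / [p̄(1 − p̄)], where f_k is the share of children in class k. Example with classes of 37/37/37/36, one class of 37 at 28.3% and the rest at 60%:
- p̄ = (110 × 0.60 + 37 × 0.283)/147 = 0.520.
- W² = [0.748 × 0.0797² + 0.252 × 0.2369²]/(0.520 × 0.480) = 0.0756, so W = 0.275.

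The value of W is essentially the same whichever class holds the 28.3%, and the test statistic carries no sign.

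**3. Simulation** (100,000 or more trials per pattern, four classes of 36-37, W=0.275). The comparison is poorest class versus all others pooled, two-sided 0.05.

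| True pattern | Chi-square significant | Comparison significant in Aim 2's direction |
|---|---|---|
| Only the poorest class low (28.3% vs 60%) | 83% | 92-93% |
| A different class low (28.3% vs 60%) | 83% | about 0.1% |
| Poorest class best (71.7% vs 40%) | 83% | 0% (93% in the opposite direction) |
| Even gradient (31.5, 43.8, 56.2, 68.5%) | 82% | 74% |
| Two classes low, two high (36.25% vs 63.75%) | 82% | 48% |

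With class sizes 21/42/42/42 the second and third rows give 83% and 84% for the chi-square, and the gradient row gives 82% against 63%.

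**4. Why the comparison's power varies.** Its noncentrality is the share of λ that lies in poorest-versus-rest. For four equal classes:
- Only the poorest differs: share 1, λ = 11.12, power 0.915.
- Even gradient (deviations −1.5, −0.5, 0.5, 1.5): share = (1.5² + 3 × 0.5²)/5 = 0.60, λ = 6.67, power 0.73.
- Two low, two high (deviations −1, −1, 1, 1): share = (1 + 3 × (1/3)²)/4 = 1/3, λ = 3.71, power 0.49.

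The comparison overtakes the 3-df test only when the share exceeds about 0.72.

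**5. Does reading the proportions suffice?** Let one other class respond best (71.7%) and the remaining three, including the poorest, share 40%. The chi-square is then significant with the poorest class observed lowest in about 26% of trials (30% if a tie counts). The prespecified comparison is significant in the predicted direction in about 19%.

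**6. Odds ratios in Section T.** ((1 + W)/(1 − W))² gives 1.49 at W=0.10 and 3.45 at W=0.30. These are the values for a 2×2 table with equal margins.

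**The case against.** The defence is substantial, and most of it stands.

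- **The test fits a stated objective.** The overarching hypothesis and the Aim 2 title are about association, and an omnibus test answers that. A reader might infer that a significant result gives no support to the study's hypothesis. That goes too far: it supports the non-directional hypothesis and leaves only the Aim 2 direction open.
- **Direction would be visible.** Proportions are to be compared class by class. A reader might set the 83% in the second row of the table against the 0.1% beside it and conclude that the chi-square misleads far more often. That is not like for like: once the poorest class is also required to be observed lowest, the chi-square figure falls to about 0.1% or less as well. Step 5 shows that inspection is a looser standard in some patterns, but the gap is moderate.
- **A two-sided comparison also rejects in the wrong direction** (93% when the poorest class responds best). It helps only if the conclusion is tied to the sign of the estimate.
- **Power.** A reader might infer that 3 df wastes power. The documents do not support that as a general claim. Section T meets its own target, and Aim 2 is also compatible with a gradient, under which the 1-df comparison is the weaker test. This is why the comparison should not replace the primary test.
- **Odds ratios.** A reader might infer that Section T understates the effect needed. It does not offer an odds ratio for W=0.275 or for a four-class table; "small effect: W=0.10, corresponding odds ratio=1.49; medium effect: W=0.30, corresponding odds ratio=3.45" only glosses Cohen's conventions. Any detectable difference in percentage points would rest on an overall response rate and a pattern that the documents do not state.

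What remains unanswered is that the plan has no prespecified analysis addressed to the Aim 2 prediction and no rule for identifying the class that it concerns.

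**Conclusion.** The primary chi-square is valid and adequately powered for the question of whether responsiveness differs among classes. It does not by itself establish Aim 2's stated hypothesis. At W=0.275 it is significant in about 83-84% of trials when another class is lowest or when the poorest class responds best, close to its rate when Aim 2 is true in its simplest form (83-84%). These percentages rest on four classes, 147 analysed children and assumed responder rates. The logical point needs none of these assumptions.

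This is a gap between hypothesis and analysis, to be closed by an addition. It is not a fault in the sample size or in the primary test. The added comparison has a limit of its own: it shows that the poorest class is below the average of the others, not below each of them, so the class proportions should still be shown.

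**What to change.** In Section U, keep the omnibus chi-square as the primary test and add for the Aim 2 hypothesis:

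1. One 1-df comparison, two-sided at 0.05: responder proportion in the class with the greatest baseline symptom burden versus all other classes pooled, reported as a difference with a 95% CI alongside the proportion in every class.
2. A written rule that identifies that class from the baseline class profiles, including what to do if no class is worst in every domain. Apply and record it before visit 2 data are merged.
3. A decision statement: Aim 2 is called supported only if the difference is significant in the predicted direction.

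Section T needs at most a note that the odds ratios 1.49 and 3.45 refer to a 2×2 table with equal margins.

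The cost is wording and one more analysis, with no new participants, visits or data. Its power should be stated openly as dependent on the pattern: at W=0.275, about 92% if only the poorest class differs, about 74% under an even gradient across equal classes (63% with sizes 21/42/42/42), and about 48% if two of four equal classes are low.
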